### 3. Study Design

#### 3.1 General Design

**Phase II Study** - This is a phase II, prospective, placebo-controlled RCT of the efficacy and safety of bupropion in combination with behavioral counseling for smoking cessation during pregnancy (see Fig. 1). Pregnant smokers (N=360) will receive bupropion or placebo treatment for 10 weeks, under strict double-blind conditions, with 3 post-treatment follow-up sessions: 2 and 6 weeks postpartum (with counseling to prevent relapse or encourage a repeat quit attempt) and monitoring of the persistence of treatment effects at 24 weeks post-TQD.

[figure not shown]
**Study Duration** – The duration of the treatment will be 10 weeks with 3 post-treatment follow-up visits: 2 weeks and 6 weeks postpartum and 24 weeks post-TQD. Birth outcomes will be obtained from labor and delivery records (permission for which will be included in the informed consent form). The entire study will run for approximately 54 months from the first participant enrolled to the last participant assessed at 24 weeks post TQD.

#### 3.2 Primary Study Endpoints

CONFIDENTIAL

This material is the property of the University of Pennsylvania. Do not disclose or use except as authorized in writing by the study sponsor

- Primary smoking status will be assessed using the Timeline Follow-back method (165) and by using carbon monoxide (CO) concentration to biochemically verify the self-report. Participants will be considered to be abstinent if they self-report abstinence (not even a puff

of a cigarette) for  $\geq 7$  days prior to the assessment after 10 weeks of treatment and at 24 weeks post-TQD and have a CO  $\leq 10$  ppm at that time (166-167). As per convention, participants are assumed to be smoking if they self-report to be smoking at the time point, cannot be reached to provide data at the time point, fail to provide a breath sample at the time point, or provide a breath sample at the time point that has a CO concentration  $> 10$  ppm (166).

- For adverse effects, our primary outcome will be the frequency of moderate or severe side effects from a checklist of bupropion-related side effects (derived from completed bupropion studies), as well as those elicited with open-ended questions, through regular obstetrics visits, and assessments triggered by any pregnancy-related complication. Adverse effects will be systematically assessed by study personnel at 5 time points over the course of the 10-week study and can trigger dose reductions or suspension of medication.
- Birth outcomes obtained from labor and delivery records (permission for which will be included in the informed consent form) will include gestational age, overall and spontaneous preterm birth (i.e., at less than 37 weeks), infant birth weight, whether small for gestational age (i.e.,  $< 10^{\text{th}}$  percentile birth weight for gestational age as determined by the Alexander curve), head circumference, Apgar scores, and NICU admissions. Obstetric complications will include type of delivery and delivery and postpartum complications.

### 3.3 Secondary Study Endpoints

Secondary smoking cessation outcomes include: smoking rate after 10 weeks of treatment and at 24 weeks post-TQD for non-abstainers, prolonged abstinence to weeks 10 and 24

CONFIDENTIAL

(defined below), continuous abstinence at weeks 10 and 24 (defined below), time to 7-day relapse (no grace period), and lapse and recovery events.

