#### 7.1.1. Aim 1:

The primary efficacy analysis (**H1**) is a comparison in week 10 (of treatment) and week 24 post-TQD of CO-confirmed 7-day point prevalence quit rates for the placebo and bupropion groups. For the week-10 comparison, we expect that the quit rates in the placebo and bupropion arms would approximate those reported in bupropion trials in the general population of smokers (i.e., placebo = 21.2%; bupropion = 35.9%, OR = 2.1; ref. 44). A sample of 360 provides 88% power to detect a significant between-group effect. The OR for bupropion treatment is similar at 24 weeks, based on Jorenby et al. (168) and our own data, and results from 10 and 24 weeks are highly correlated ( $\rho > 0.7$ ). Thus, we have 80% power to detect a significant difference between treatment arms.

Safety analyses (**H2**) will examine maternal safety across the 10-week treatment and 24-week follow-up periods and fetal and birth outcomes. Key maternal and fetal outcomes to be compared across treatment groups include rates of moderate-to-severe side AEs of bupropion (from the AE checklist). Key birth outcomes will include Apgar scores, birth weight, duration of pregnancy, rate of obstetrical complications, and need for NICU admission. These analyses will involve a test of equivalence because we cannot use standard statistical tests to conclude that a non-significant comparison shows that the drug is safe (i.e., "the absence of evidence is not evidence of its absence"). In our past study with bupropion, 45% of bupropion-treated participants reported no moderate-to-severe AEs, vs. 47% of participants on placebo, a 2% difference. With the present sample size, we will have 82% power to detect similar equivalence between treatment arms on the frequency of moderate-to-severe AEs over the course of the trial, given that AEs are not significantly different between treatment arms, using an equivalence window of 0.30 to 0.60. Likewise, Oncken et al. (47) reported 38% AEs for the placebo group

CONFIDENTIAL

and 25% in the nicotine group. An equivalence test with placebo and bupropion groups both at 30% and an equivalence window for bupropion of +/-15% provides 81% power.

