## **7.2. Statistical Analyses**

[name] will oversee analyses, which will be conducted using Stata, SAS, or R-Language software. Preliminary analyses will assess sample characteristics (e.g., dependence, race) by treatment using t-test or contingency table methods. These variables will also be examined for their relationship to completion of outcome assessments. Variables related to treatment arm or completion of follow ups will be included as covariates in analyses of study aims. Compliance measures will be evaluated across treatment arms, and controlled for in primary analyses. We will examine the correlation between self-report and pill count data and week-5 bupropion plasma levels. We will use intent-to-treat as the primary method to evaluate study aims.

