### **7.2.2. Specific Aim 1: To compare the efficacy of bupropion with placebo for smoking cessation in pregnant smokers.**

For **H1**, we will test for treatment group differences in a binary abstinence outcome that is a repeated measure using a generalized estimating equations (GEE) model with a logit link. Quit rates at the end of week 10 of treatment and 24 weeks post-TQD will represent our primary outcome variables. Medication group (bupropion vs. placebo) and time point (end of week 10 of treatment and 24 weeks post-TQD) will be treated as categorical predictor variables, and the model will predict separate effects of treatment on abstinence at each time point (an interaction). Our initial analyses will be stratified by site, and we will carefully examine the models for differences by site, testing for an overall interaction. We will use baseline depression (PHQ-9 score of 10) to stratify the randomization. The model may include a small number of covariates added to control error or adjust for confounding [e.g., age, history of pre-term delivery, baseline gestational age, daily smoking rate]. Any variables found to be associated with both outcome and treatment assignment will be entered as covariates. In the absence of an overall interaction (by site), we will pool the study population and account for site in the model as a binary predictor. To evaluate the effectiveness of randomization, we will compare summary statistics for participant characteristics in the two study arms. If there is an imbalance in participant characteristics, statistical adjustment will be used to ensure that the initial results were not biased by it.

Because many participants will fail to become completely abstinent, but may show a reduction in smoking, we will examine cigarette consumption as a secondary outcome. The analysis will be similar to the primary analysis, except that we examine the effect of treatment arm on daily cigarette counts using a GEE model with a negative-binomial link. Likewise, time to (recurrent) event models will be fitted using Cox regression, stratified by event sequence, as in Schnoll et al. (52), to assess lapse and recovery events over 24 weeks.

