### **7.3. Participant Population for Analysis**

Data from protocol-compliant participants will be used for analysis.

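### Section 3.3 limits the smoking-rate endpoint to non-abstainers while 7.2.2 does not; the restricted arm comparison is not protected by randomisation and can be biased

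*Combined protocol and SAP*

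**What the plan says.** Section 3.3, which lists the secondary smoking outcomes, includes "smoking rate after 10 weeks of treatment and at 24 weeks post-TQD for non-abstainers". Section 3.2 defines abstinence as 7 days of self-reported abstinence confirmed by breath CO. It classes as smoking any woman who reports smoking, cannot be reached, gives no breath sample, or has a CO above 10 ppm. The non-abstainers are therefore everyone who does not meet the primary outcome at that time point.

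Section 7.2.2 introduces the same outcome by noting that many women will not stop completely but "may show a reduction in smoking, we will examine cigarette consumption as a secondary outcome". On the method it says: "The analysis will be similar to the primary analysis, except that we examine the effect of treatment arm on daily cigarette counts using a GEE". The link is to be negative-binomial. The section names no subgroup, does not say that abstainers enter as zero, and gives no count for women classed as smoking by default.

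On the general population, section 7.2 says "We will use intent-to-treat as the primary method to evaluate study aims", whereas section 7.3 says "Data from protocol-compliant participants will be used for analysis".

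For week 10, section 7.1.1 assumes "placebo = 21.2%; bupropion = 35.9%, OR = 2.1; ref. 44" and expects a similar odds ratio at 24 weeks.

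**The concern.** Abstinence status is measured after randomisation, and the trial is designed on the expectation that treatment changes it. Comparing arms only among women who did not quit compares two groups filtered at different rates. If bupropion works, some women who quit because of it leave the bupropion group, while their counterparts on placebo remain. If those women would have smoked more or less than the others, the two group means differ even when the drug does nothing for women who continue to smoke.

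Two things are at stake. The restricted contrast mixes any real effect on consumption with this selection. It also discards the part of the reduction in smoking that comes from quitting. Because 3.3 and 7.2.2 differ on who is included, an analyst could follow either one and claim to have followed the plan.

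**Working it through.** **Inputs from the documents.** 180 women per arm (5.3); week-10 abstinence 21.2% on placebo and 35.9% on bupropion (7.1.1); two-sided alpha 0.05 (7.1); quit rates under behavioural intervention of 20%, 15% and 5% at under 10, 10 to 19 and over 20 cigarettes per day (1.1, Behavioral Interventions). The documents give no distribution of cigarettes per day for this trial, so every consumption figure below is an assumption.

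**Step 1. The plan's own figure.** The plan states: "A sample of 360 provides 88% power to detect a significant between-group effect". Unpooled check: SE = √(0.212×0.788/180 + 0.359×0.641/180) = 0.0470; 0.147/0.0470 − 1.96 = 1.17; power 87.9%. With pooled variance it is 87.3%. The 88% reproduces, so these are the rates on which the trial was sized. No power or effect size is given for the smoking-rate endpoint.

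**Step 2. Size of the selection at week 10.**
- Placebo non-abstainers: 180 × 0.788 = 142.
- Bupropion non-abstainers: 180 × 0.641 = 115.
- If the drug only adds quitters, the share of women who would be non-abstainers on placebo but are missing from the bupropion subgroup is 0.147/0.788 = 18.7%.

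The 24-week rates are not given. A similar odds ratio implies selection of the same kind there.

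**Step 3. What decides the sign.** Suppose the extra quitters would have smoked x per day and all other non-abstainers smoke 9 (both assumed), with no drug effect on women who continue. The placebo non-abstainer mean is (0.147x + 0.641×9)/0.788, and the bupropion mean is 9.0.

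| x | Placebo mean | Bupropion mean | Bupropion/placebo |
|---|---|---|---|
| 4 | 8.07 | 9.0 | 1.12 |
| 7 | 8.63 | 9.0 | 1.04 |
| 9 | 9.00 | 9.0 | 1.00 |
| 12 | 9.56 | 9.0 | 0.94 |

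The shift can go against the drug, be nil, or favour it. The x = 4 row is extreme because every extra quitter is a light smoker.

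**Step 4. Using the quit-rate gradient in 1.1.** Take the 20/15/5% rates for placebo and apply an odds ratio of 2.1 in each stratum (34.4%, 27.0%, 10.0% on bupropion). Assume stratum means of 6, 13 and 22 per day. Overall quit rates are then 15% to 17% on placebo and 27% to 30% on bupropion, somewhat below those in 7.1.1.

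| Assumed mix (light/mid/heavy, %) | Non-abstainer mean, placebo vs bupropion | Ratio | All-randomised mean (abstainers = 0) | Ratio |
|---|---|---|---|---|
| 60/30/10 | 9.98 vs 10.23 | 1.025 | 8.28 vs 7.19 | 0.867 |
| 50/40/10 | 10.67 vs 10.91 | 1.022 | 8.91 vs 7.74 | 0.869 |
| 40/40/20 | 12.38 vs 12.71 | 1.027 | 10.52 vs 9.33 | 0.887 |

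**Step 5. Using the quit rates in 7.1.1.** Assume gamma-distributed baseline cigarettes per day (mean 8, SD 5, or mean 10, SD 6, floored at the entry minimum of 3). Assume a 40% cut in both arms among continuing smokers, so there is no drug effect on them. Vary the odds ratio for quitting per SD of log consumption.

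| Odds ratio per SD | Non-abstainer ratio | Approximate rejection rate, nominal 5% | All-randomised ratio |
|---|---|---|---|
| 1.0 | 1.00 | 5% | 0.81 |
| 0.7 | about 1.03 | about 7% | about 0.84 |
| 0.5 | about 1.05 | about 11% | about 0.85 |

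The rejection rates come from a normal approximation to a difference in means, not from the planned GEE. In steps 4 and 5 the all-randomised mean is about 11% to 19% lower on bupropion, and the restricted comparison shows none of that reduction.

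**The case against.** The strongest reply is that 3.3 only lists an outcome and 7.2.2 is the analysis. Section 7.2.2 models cigarette counts by arm in the manner of the primary analysis, which includes everyone under intent-to-treat. Its remark about women who do not fully stop explains why consumption is examined and does not define an analysis set. A negative-binomial model accepts zeros. On that reading the plan already does most of what is asked here.

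Much of this stands. A reader of 3.3 alone might infer that the plan commits to a biased arm comparison. The documents do not support that: the restricted comparison is one reading of two sections that have not been reconciled. But 7.2.2 does not state a population for this outcome or say that abstainers count as zero, and its motivation also fits the subgroup in 3.3. Section 7.3 then points away from intent-to-treat. The only explicit statement of who is included for this endpoint is the restriction itself.

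A reader might also infer that an effective drug would be made to look harmful. That is not established either. Bias needs a link between drug-induced quitting and consumption. The gradient in 1.1 comes from behavioural interventions. All women here receive counselling, so it is relevant, but it does not show who quits because of bupropion. Section 1.1 also reports a bupropion trial in which fast metabolisers of nicotine had high quit rates only on the drug, and it does not say whether such women smoke more or less. The direction is therefore open.

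**Conclusion.** The point holds as a conflict between 3.3 and 7.2.2 that should be resolved before analysis. If 3.3 is followed, the arms are compared in groups formed after randomisation, expected at about 142 and 115 women at week 10, and the contrast can be biased. Under the assumed consumption distributions with lighter smokers quitting more, the shift is about 2% to 5% against bupropion. It is zero if quitting is unrelated to consumption or if treatment does not affect abstinence, and it reverses if the extra quitters are heavier smokers. These sizes rest on assumed cigarettes-per-day distributions and on no drug effect among women who continue to smoke. The loss of the reduction due to quitting does not depend on the direction of selection.

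This is a secondary endpoint with no power claim. H1, its stated 88% power and the sample size of 360 are unaffected.

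**What to change.** - In 3.3, delete the restriction to non-abstainers from the smoking-rate endpoint.
- In 7.2.2, state that cigarettes per day are analysed in all randomised women, with confirmed abstainers counted as zero, using the planned negative-binomial GEE. Naming the population here also settles, for this outcome, the disagreement between 7.2 and 7.3.
- State how the count is set for women classed as smoking because they were unreachable, gave no breath sample, or reported zero cigarettes with a CO above 10 ppm, and add a sensitivity analysis of that rule. Counting abstainers as zero does not cover these women. The imputation in 7.2.1 is written for items missing within assessments, not for a woman with no assessment.
- Report the non-abstainer mean by arm as descriptive only, without a test.

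The cost is a wording change and a small amount of extra analysis for the missing-count rule. No new data collection is needed: Table 2 already schedules the Timeline Follow-back at week 10 and week 24.

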### **3.4 Safety Endpoints**

Participants with severe psychological symptoms (e.g., suicidal thoughts), experiencing a serious adverse event that the Principal Investigator believes to be related to study drug and a potential threat to the health and safety of the participant or fetus will be withdrawn from the study (see section 8.1).

## **4. Participant Selection and Withdrawal**

### **4.1. Inclusion Criteria**

1. Currently smoking on average 3 or more cigarettes per day for the preceding 7 days with a breath CO of at least 5 ppm and wants to quit smoking
2. Pregnant at 13-26 weeks gestation (to maximize safety and the likelihood of receiving 10 weeks of treatment)
3.  $\geq 18$  years of age
4. Able to speak and read English at a 6th grade level or higher, using the Slosson Oral Reading Test (SORT)
5. Committed to remaining in the geographic area for at least 3 months postpartum
6. Able to sign written informed consent and commit to completing the procedures involved in the study.
7. Methadone or buprenorphine-maintained women must be in methadone or buprenorphine treatment for a minimum of 2 weeks prior to entering the study. Their 2 most recent urine drug screens, consecutive and administered at least one week apart, must both be positive for methadone or buprenorphine and negative for drugs of abuse other than cannabis. Participants who screen positive for other drugs at either time point will not be enrolled in the study until they meet this criterion.

### **4.2. Exclusion Criteria**

1. During the last 90 days from screening visit, meets any criteria for a DSM-IV diagnosis of drug or alcohol dependence—excluding tobacco or cannabis dependence and, for methadone or buprenorphine maintenance patients, opioid dependence—**AND** either evidences ongoing use of illicit drugs other than cannabis or continues to abuse or misuse prescription drugs such as CNS stimulants.
2. Pregnant with triplets or higher order multiples
3. Has an unstable psychiatric disorder (i.e., suicide risk moderate or severe, as reflected by a score of  $\geq 9$  on the MINI Section B (Suicidality) or a suicide attempt during the preceding year, psychiatric hospitalization within the last 3 months; current psychotic disorder based on the MINI)
4. Current or past Bipolar Disorder as determined by a study psychiatrist or psychologist based on assessment with the MINI, relevant information from the medical record and, when warranted, direct clinical evaluation.
5. Current, regular use of psychotropic medication, inhibitors of CYP2B6 (e.g., ticlopidine, clopidogrel), inducers of CYP2B6 (e.g., ritonavir, lopinavir, efavirenz), anticonvulsants (e.g., carbamazepine, phenobarbital, phenytoin), beta-blockers (e.g., metoprolol), Type 1C antiarrhythmics (e.g., propafenone and flecainide), drugs that require metabolic activation by CYP2D6 to be effective (e.g., tamoxifen), drugs that lower seizure

CONFIDENTIAL

- threshold (e.g., antipsychotics, tricyclic antidepressants, theophylline, or systemic corticosteroids), levodopa or amantadine
6. Current unstable medical problems or potential inability to tolerate study treatment [e.g., threatened abortion: current persistent hyperemesis gravidarum (HEG) requiring intravenous fluids (to be rescreened when HEG is stabilized/resolved and no electrolyte abnormalities are evident); hypertension with evidence of end organ dysfunction or on more than 2 medications at the start of the pregnancy]; arteriovenous malformation; AIDS; laboratory evidence of hepatic impairment (e.g. viral hepatitis with serum transaminase levels more than twice the upper limit of normal) ; renal impairment (e.g., elevated creatinine or creatinine clearance <75cc/hr), metabolic disorders (e.g., hypoglycemia, hyponatremia) or end organ damage from any chronic medical condition (e.g. abnormal pulmonary function tests), glaucoma, or other significant medical problems that in the opinion of a study obstetrician makes the risk of study participation unacceptable.
  7. Known major fetal congenital malformation—as determined by the study obstetrician—diagnosed prior to study randomization
  8. History of seizure disorder
  9. Current use of a smoking cessation medication in addition to the study medication, such as nicotine replacement therapy
  10. Current or history of bulimia or anorexia nervosa
  11. Current use of tobacco products other than cigarettes (e.g., E-cigarettes)
  12. Current clinically significantly abnormal laboratory evaluations that are not adequately controlled by standard of care treatment.
  13. History of severe head injury (i.e., with loss of consciousness)
  14. Any medical condition or concomitant medication that could compromise subject safety or treatment, as determined by the Principal Investigator and/or Study Physician.
  15. Inability to provide informed consent or judged by the Principal Investigator and/or Study Physician to be an unsuitable candidate for a clinical drug trial.

### **4.3. Participant Recruitment and Screening**

All sites will have a senior clinician to oversee the integration of the trial into clinical practice. Approval from the City of Philadelphia Institutional Review Board and the Health Commissioner's Office will be obtained given the involvement of Philadelphia Department of Public Health data, staff, and clients at the Jefferson MATER site, where methadone-maintained pregnant smokers will be enrolled. Buprenorphine-treated subjects will be recruited from the "Mothers MATTER" program at the Dickens clinic and from the Jefferson MATER site. As in our previous successful clinical trials (e.g., 14, 47, 52), we will use experienced and trained research staff to identify and screen potentially eligible participants in the clinics. Recruitment sites will also be provided with IRB-approved materials designed to raise awareness of the study, including posters and brochures to be displayed prominently in all clinic areas. We will also encourage referrals from clinicians in the surrounding areas at each site, and will recruit through newspapers, maternity magazines and social media. Interested and potentially eligible participants will be scheduled for an intake session (week -1) to determine eligibility. For details on Screening, see 6.2 Informed Consent and Screening Visit below.

